--	---

	
endpoint value as a covariate. Results from each complete dataset will be combined to provide the adjusted mean change from Baseline to Week 26 for each treatment group, as well as the between-group difference (comparing sotagliflozin vs placebo) and the 95% CI for the difference.
 
The categorical secondary efficacy variables of HbA1c <6.5%, <7% at Week 26 will be analyzed using a Cochran-Mantel-Haenszel method stratified by randomization stratum of HbA1c ($\leq 8.0\%$, $>8.0\%$), and randomization stratum of SBP (<130, ≥ 130 mmHg).
 
Analysis of other efficacy endpoints:
 
The analysis of other endpoints will be descriptive with no formal testing. Summary statistics at scheduled visits using OC will be provided by each treatment group. Graphical presentations will also be used to illustrate trends over time.
 
Analyses of safety data:
 
All safety summaries will be descriptive; no statistical significance tests will be performed on safety data. These analyses will be based on the Safety Population, which is defined as all randomized patients who receive at least 1 dose of double-blind treatment, regardless of the amount of treatment administered. Patients will be analyzed for safety analyses according to the treatment actually received. The safety analyses will be provided for the 26-week core treatment period and for the entire treatment period.
 
Analysis of ABPM substudy endpoints:
 
ABPM substudy endpoints will be analyzed using a similar approach as the primary efficacy endpoint with missing values imputed by control-based multiple imputation method under the missing not at random frame work. Each of the complete dataset will be analyzed using ANCOVA model including factors for treatment (sotagliflozin, placebo), randomization stratum of HbA1c ($\leq 8.0\%$, $>8.0\%$) as fixed effects, and the baseline value of the specific dependent variable as a covariate.

DURATION OF STUDY PERIOD (per patient)	Up to 87 weeks, including a Screening Period consisting of a Screening phase of up to 2 weeks and a 2-week single-blind Run-in phase, a 26-week double-blind Core Treatment Period, a 53-week double-blind Extension Period, a 4-week post treatment Follow-up period to collect safety information.

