8.2.2 Rescue therapy

The threshold values are defined as follows, depending on study period:

- FPG >270 mg/dL (15.0 mmol/L) from Randomization up through the scheduled Week 8 Visit
- FPG >240 mg/dL (13.3 mmol/L) after the Week 8 visit up through the scheduled Week 12 Visit
- FPG >200 mg/dL (11.1 mmol/L) after the Week 12 Visit through the end of the 26-week Core Treatment Period
- FPG >170 mg/dL (9.4 mmol/L) or HbA1c \geq 8.0% after the Week 26 Visit through the end of the treatment period

Routine fasting SMBG (see [Section 9.2.1.6](#)) and central laboratory alerts on FPG (and HbA1c at Week 26 and onward) are set up to ensure that glycemic parameter results remain under predefined thresholds.

- If one fasting SMBG value exceeds the specific glycemic limit on one day, the patient checks it again during the two following days. If all the values in three consecutive days exceed the specific limit, the patient should contact the Investigator and a central laboratory FPG measurement (and HbA1c at Week 26 and onward) be performed as soon as possible, preferably within 7 days, to confirm the hyperglycemia.
- Upon receipt of a central laboratory rescue alert, a central laboratory re-test must be completed and confirmed as exceeding the threshold for rescue before rescue therapy is initiated. The re-test confirmation should be performed as soon as possible, but within 7 days of receipt, by unscheduled visit.

In the event that a confirmatory FPG and/or HbA1c exceeds the threshold, the Investigator should ensure that no reasonable explanation exists for insufficient glucose control and in particular that:

- The increased FPG has been tested at a fasting status (ie, no food intake for \geq 8 hours)
- Investigational medicinal product is given at the planned dose
- There is no intercurrent disease, which may jeopardize glycemic control (eg, infectious disease)
- Compliance to treatment is appropriate
- Compliance to diet and lifestyle is appropriate

If any of the above can reasonably explain the insufficient glycemic control, the Investigator should consider not initiating rescue medication and should undertake appropriate action, ie:

- Assess plasma glucose in fasting condition (ie, after at least 8 hours fast)
- Initiate an evaluation and treatment of intercurrent disease (to be reported in AE/concomitant medication parts of the e-CRF and the medical record)
- Stress the absolute need to be compliant with treatment

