8.8.1 Prohibited prior and concomitant medications

During the study treatment period, the following medications are prohibited:

- Initiation of any antidiabetic agents, including oral or injectable antihyperglycemic agents other than the IMP is not allowed before the rescue therapy
- Systemic use of glucocorticoids is not allowed for more than 10 consecutive days (topical, ophthalmic, nasal spray or inhaled applications are allowed)
- Initiation of any weight loss drugs (eg, phentermine, orlistat)
- Investigational medicinal products in any other clinical study
- SGLT2 inhibitors (eg, canagliflozin, dapagliflozin, or empagliflozin) are not allowed for rescue

Reduction of digoxin dose should be considered because sotagliflozin acts as a weak P-gp inhibitor and increases systemic exposure to digoxin. Patients taking sotagliflozin with concomitant digoxin should have digoxin concentrations monitored and doses reduced as needed. In addition, other P-gp substrates may be affected and the labels of P-gp substrate drugs should be consulted with regards to monitoring and dose adjustments.

Other medications which are unlikely to interfere with the PK or PD of the IMP or confound interpretation of the study endpoints are allowed as needed following discussion between the Investigator and the Sponsor. However, doses of chronically administered medicines should be kept fixed during the trial if at all possible.

After premature permanent discontinuation of the IMPs, any treatments (other than SGLT2 inhibitors) are permitted, as deemed necessary by the Investigator.

The dose of all antihypertensive agents should be kept constant during the 12 weeks following randomization and no antihypertensive agents should be added or withdrawn for the 12 weeks following randomization unless it is considered necessary for safety reasons.

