11.4.3 Analyses of safety data

Safety endpoints are presented in [Section 9.2](#). The summary of safety results will be presented by treatment group. The safety data will be summarized for the 26-week Core Treatment Period and the entire treatment period separately, unless specified otherwise. All safety analyses will be performed on the Safety population as defined in [Section 11.3.2](#) using the following common rules:

The following definitions will be applied to laboratory parameters and vital signs:

- The potentially clinically significant abnormality (PCSA) values for clinical laboratory tests and vital signs are defined as abnormal values considered medically important by the Sponsor's Global Pharmacovigilance and Epidemiology department and in effect at the time of the final SAP approval. PCSA criteria for parameters not cited in the protocol as safety parameters will not be analyzed,
- PCSA criteria will determine which patients had at least 1 PCSA during the on-treatment period, taking into account all evaluations performed during the on-treatment period, including unscheduled or repeated evaluations. The number of all such patients will be the numerator for the on-treatment PCSA percentage.

The "observation periods" defined in [Section 9.2.1](#) are applicable for classification of AEs, determination of on-treatment PCSA values and the last on-treatment value for the laboratory, vital sign and ECG parameters.

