11.4.3.4 Analyses of events of special interest

The number (%) of patients with each EOSI event will be summarized by treatment group. All events reported by the Investigators on the AE forms for special interests will be listed along with the adjudication outcome (if applicable).

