2.4.5 Analyses of safety data

Safety endpoints are presented in [Section 2.1.4](#). The summary of safety results will be presented by treatment group. The safety data will be summarized for the 26-week core treatment period and the 79-week entire treatment period separately, unless otherwise specified.

The “observation period” defined in [Section 2.1.4](#) is applicable in all safety analyses for the classification of AEs, determination of treatment-emergent Potentially Clinically Significant Abnormality (PCSA) values and the last on-treatment value for the laboratory, vital sign and ECG.

General common rules

All safety analyses will be performed on the Safety population using the following common rules:

- Safety data in patients who do not belong to the safety population (eg, exposed but not randomized) will be listed separately.
- The baseline value (with the exception of serum creatinine and eGFR) is defined as the last available value before the first dose of double-blind IMP. For creatinine and eGFR, the baseline value is defined as the average of all values before the first dose of double-blind IMP.
- PCSA values are defined as abnormal values considered medically important by the Sponsor according to predefined criteria/thresholds based on literature review and defined by the Sponsor for clinical laboratory tests, vital signs, and ECG (Appendix E).
- PCSA criteria will determine which patients had at least 1 PCSA during the treatment-emergent AE period, taking into account all evaluations performed during the treatment-emergent AE period, including nonscheduled or repeated evaluations. The number of all such patients will be the numerator for the treatment-emergent PCSA percentage.
- The treatment-emergent PCSA denominator by group for a given parameter will be based on the number of patients assessed for that given parameter during the treatment-emergent AE period by treatment group in the safety population.
- For laboratory parameters cited in the protocol as efficacy endpoints (including HbA1c and plasma glucose, etc), PCSA summaries will not be provided. These parameters will be summarized in [Section 2.4.4](#). For serum creatinine, and eGFR, PCSA summaries will be presented in safety [Section 2.4.5](#), while descriptive summaries in efficacy [Section 2.4.4](#).

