- All treatment-emergent SAEs by primary SOC, HLGT, HLT, and PT, showing the number (%) of patients with at least 1 serious treatment-emergent AE, sorted by the internationally agreed SOC order. The other levels (HLGT, HLT, PT) will be presented in alphabetical order.
- All treatment-emergent SAEs regardless of relationship and related to IMP, by primary SOC, HLGT, HLT, and PT, showing the number (%) of patients with at least 1 treatment-emergent SAE, sorted by the internationally agreed SOC order. The other levels (HLGT, HLT, PT) will be presented in alphabetical order.

Analysis of all treatment-emergent AE(s) leading to treatment discontinuation

- All treatment-emergent adverse events leading to treatment discontinuation, by primary SOC, HLGT, HLT, and PT, showing the number (%) of patients sorted by the internationally agreed SOC order. The other levels (HLGT, HLT, PT) will be presented in alphabetical order.

Analysis of adverse events of special interest

The summaries of AESI will be presented for the 79-week entire treatment period only in the safety population.

Pregnancy and overdose will be included in overall AE summaries if any are reported. ALT increase >3 x ULN is included in laboratory PCSA summary if any.

In addition, the number (%) of patients with an AESI will be summarized by PT and by treatment group during the 79-week entire treatment period only. Corresponding listings will be provided as appropriately.

Analysis of events of special interest

The summaries of EOSI will be presented for the 79-week entire treatment period only in the safety population.

CV events, bone fracture and DKA

For EOSIs that are adjudicated (ie, deaths, myocardial infarction, stroke, and unstable angina requiring hospitalization, heart failure requiring hospitalization, bone fracture, and diabetic ketoacidosis), the number (%) of patients with an EOSI positively adjudicated by CEC will be summarized by treatment group. All EOSIs sent for adjudication and/or reported by the investigators in the specific AE forms will be listed along with the adjudication outcome.

Renal events

For the EOSI renal events where selected events are adjudicated, the number (%) of patients with any renal events identified in [Table 3](#) in [Section 2.1.4.2](#) will be summarized by treatment group.

The following renal events will be listed along with the adjudication outcome if applicable, including events,

- i. recorded in eCRF “GFR decrease”,

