- ii. recorded in eCRF “Renal Event – Dialysis”,
- iii. identified as “Renal transplant” in eCRF “Other procedure”,

Renal death will be part of all deaths specified above.

Other EOSIs

For EOSIs that are not adjudicated, the number (%) of patients with at least one event will be summarized by treatment group and by PT (as identified in [Table 3](#) in [Section 2.1.4.2](#)).

Severe hypoglycemia will be included in the summary of hypoglycemia (See [Section 2.4.5.1](#)).

AE leading to an amputation is described in the section below.

Analysis of Amputation

The number (%) of patients with amputation will be summarized by treatment group and by PT and LLT during the study (ie, regardless of on- or post-treatment). Amputation is a procedure recorded in eCRF form “Other Procedures related to Amputation”. Patients who had a procedure related to amputation will be listed.

The number (%) of patients with an “AE leading to an amputation” will be summarized by treatment group and by PT. The “AE leading to an amputation” is determined by the AE identifier recorded in eCRF “Other Procedures related to Amputation” when “AE correction” is chosen as the reason for the amputation procedure.

In addition, the number (%) of patients with an “AE potentially leading to an amputation” will be summarized by treatment group and by PT (as identified in [Table 3 in Section 2.1.4.2](#)). These PTs in [Table 3](#) were requested by the European Medicines Agency (EMA)/ Pharmacovigilance Risk Assessment Committee (PRAC) Assessment Report, 9 February 2017). The associated list will be provided as well, with patients who had an amputation procedure flagged. “AE potentially leading to an amputation” represents the condition that may potentially lead to the amputation procedure, but not in all cases an amputation has occurred.

Analysis of pretreatment and posttreatment AEs

- All pretreatment AEs by primary SOC and PT, showing the number (%) of patients with at least 1 pretreatment AE, sorted by the internationally agreed SOC order and decreasing incidence of PTs within each SOC in the sotagliflozin group
- All posttreatment AEs by primary SOC and PT, showing the number (%) of patients with at least 1 posttreatment AE, sorted by the internationally agreed SOC order and decreasing incidence of PTs within each SOC in the sotagliflozin group.

Listings

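### Grouped, renal and adjudicated events of special interest are tabulated over 79 weeks only, with no 26-week core table

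*SAP*

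**What the plan says.** The protocol synopsis states the general rule without qualification: "The safety analyses will be provided for the 26-week core treatment period and for the entire treatment period". Protocol 11.4.3 repeats it with room for exceptions: "The safety data will be summarized for the 26-week Core Treatment Period and the entire treatment period separately, unless specified otherwise". SAP 2.4.5 does the same: "The safety data will be summarized for the 26-week core treatment period and the 79-week entire treatment period separately, unless otherwise specified". The protocol's own EOSI section, 11.4.3.4, names no period: "The number (%) of patients with each EOSI event will be summarized by treatment group".

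SAP 2.4.5.2 then makes the exception: "The summaries of EOSI will be presented for the 79-week entire treatment period only in the safety population". Under that sentence stand three sets of tables:
- cardiovascular events, fracture and diabetic ketoacidosis, counted when positively adjudicated;
- renal events;
- non-adjudicated groups such as genital mycotic infection, urinary tract infection, volume depletion, diarrhea, pancreatitis, venous thrombosis and selected malignancies.

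Two items are routed elsewhere. "Severe hypoglycemia will be included in the summary of hypoglycemia", which SAP 2.4.5.1 runs on the treatment-emergent periods, with only the Kaplan-Meier curve confined to 79 weeks. Amputation procedures are summarized over the whole study.

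The rescue criteria in protocol 8.2.2 change at Week 26. From Week 12 to Week 26 the trigger is FPG above 200 mg/dL. The trigger of FPG above 170 mg/dL or HbA1c of at least 8.0% applies "after the Week 26 Visit through the end of the treatment period".

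**The concern.** Protocol 4.6 lists most of these events as identified or potential risks to be watched closely. The core period is the part of the trial nearest to a plain comparison of sotagliflozin with placebo on metformin. In the extension the rescue trigger is lower and any approved class except SGLT2 inhibitors may be added. Events unrelated to treatment also go on accumulating in both arms.

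The planned EOSI output is the number and percentage of patients by arm. Rates per patient-year, which SAP 2.4.5.1 gives for hypoglycemia, are not planned for EOSIs. If an excess of, say, diarrhea or volume depletion arises early, the trial report would contain no EOSI table for the period in which it arose. The stake is how readable the safety comparison is. No hypothesis test or decision rule depends on it.

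**Working it through.** **1. Length of the two periods.** Protocol Table 1 gives a 26-week core and a 53-week extension: 26 + 53 = 79 weeks, as stated. Share of planned time after Week 26: 53/79 = 67.1%. By the visit days in the flow chart: (551 − 182)/551 = 67.0%.

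**2. Share of time on treatment.** The documents give no discontinuation rate. Assume a constant hazard h with a proportion d off treatment by Week 79, so h = −ln(1 − d)/79. The share of on-treatment time after Week 26 is 1 − (1 − e^(−26h))/(1 − e^(−79h)). For d from 0% (the limiting case) to 40% this runs from 67.1% down to 61.3%. Two-thirds is right for planned time and slightly high for person-time.

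**3. Can the core adverse event tables supply the missing counts?** SAP 2.4.5.2 plans core-period tables by system organ class, high-level group term, high-level term and preferred term.
- Grouped EOSIs: Appendix F lists 35 preferred terms (by count) for volume depletion. SAP Table 3 defines diarrhea as a narrow standardised query plus six further terms. One patient may have several of these terms, for example dehydration and hypotension, so rows cannot be added to give patients with at least one event. The higher-level rows count across related terms, but nothing in the SAP aligns them with the EOSI lists.
- Adjudicated EOSIs: SAP Table 3 counts cardiovascular events, fracture and ketoacidosis only on a positive committee decision. The adverse event tables do not apply that filter.
- Renal EOSIs: these rest on sustained eGFR criteria, dialysis lasting at least 90 days, transplant or renal death, taken from dedicated forms or adjudication. The adverse event tables do not apply these criteria either.

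The core tables show the components but not these counts.

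**4. Illustration of dilution (every input assumed).** Take a core-period risk of 4% on placebo and 8% on sotagliflozin: risk ratio 2.0, difference 4.0 points. Assume no further drug excess and the same extension background risk b in both arms. The 79-week risk is 1 − (1 − core)(1 − b).
- b = 4%: placebo 1 − 0.96 × 0.96 = 7.84%; sotagliflozin 1 − 0.92 × 0.96 = 11.68%; ratio 1.49, difference 3.84 points.
- b = 8%: placebo 1 − 0.96 × 0.92 = 11.68%; sotagliflozin 1 − 0.92 × 0.92 = 15.36%; ratio 1.32, difference 3.68 points.

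Now assume also that 40% of placebo and 20% of sotagliflozin patients are rescued, 25–50% of them with a drug that causes the event in 10–20%. This multiplies in a further factor (1 − r).
- Mildest case: r = 0.40 × 0.25 × 0.10 = 1.0% on placebo and 0.5% on sotagliflozin. With b = 4%, the risks are 1 − 0.96 × 0.96 × 0.99 = 8.76% and 1 − 0.92 × 0.96 × 0.995 = 12.12%; ratio 1.38, difference 3.36 points.
- Strongest case: r = 0.40 × 0.50 × 0.20 = 4.0% on placebo and 2.0% on sotagliflozin. With b = 8%, the risks are 1 − 0.96 × 0.92 × 0.96 = 15.21% and 1 − 0.92 × 0.92 × 0.98 = 17.05%; ratio 1.12, difference 1.84 points.

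Background accumulation alone lowers the ratio but leaves the difference almost intact. The difference shrinks materially only if rescue itself adds events, and more of them on placebo.

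**The case against.** The case for leaving the plan as it is has real substance.

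- **The exception is permitted and openly stated.** Both protocol 11.4.3 and SAP 2.4.5 allow it, and the SAP treats adverse events of special interest the same way. A reader might infer that the SAP breaches the protocol. The documents do not support that: only the synopsis omits the exception clause. Some rows of the SAP change tables are redacted, so the absence of a visible reason does not show that none existed.
- **79 weeks matches the safety objective**, which covers the whole trial. The on-treatment period is defined regardless of rescue. Counting events after rescue is the declared approach. This justifies keeping the 79-week table, but it is no argument against a core table beside it.
- **Core-period information does exist.** A reader might infer that these harms are compared only over 79 weeks. In fact the core adverse event tables go up to high-level group terms, abnormal blood pressure, creatinine and eGFR values fall under the two-period default, and listings carry onset dates. An early excess in diarrhea terms would probably be noticed. What is missing is the grouped and adjudicated count.
- **The core period is cleaner, not clean.** Rescue is allowed in it, with thresholds tightening after Weeks 8 and 12. Protocol 8.8.1 says "no antihypertensive agents should be added or withdrawn for the 12 weeks following randomization", apart from safety reasons, so the remaining 26 − 12 = 14 core weeks have the same freedom as the extension.
- **No test is affected.** SAP 2.4.5 makes safety essentially descriptive, with relative risks optional.

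These points reduce the weight of the concern; the missing count remains.

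**Conclusion.** The point holds in limited form. For grouped, renal and adjudicated EOSIs, other than severe hypoglycemia and amputation procedures, the plan gives no number of patients with at least one event in the core period, and no other planned table supplies it. This departs from the unqualified synopsis sentence, though it falls within the exception clause elsewhere. The only EOSI comparison spans a period of which 53/79 (67%) follows the Week 26 rescue change, or 61–67% of person-time if up to 40% are assumed to stop treatment.

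A reader might go further and infer that sotagliflozin harms will be diluted or masked. The documents do not support that. They give no rescue or EOSI rates by arm, so neither size nor direction of distortion can be computed. The illustrated fall in risk ratio from 2.0 to between 1.1 and 1.5 rests wholly on assumed inputs. Without a rescue effect the risk difference stays at 3.7–3.8 points against 4.0. With safety descriptive, this is a minor-to-moderate improvement.

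**What to change.** Amend the sentence in SAP 2.4.5.2 so that the adjudicated, renal and non-adjudicated EOSI summaries are presented for the 26-week core period and for the 79-week entire period, using the core treatment-emergent window already defined in SAP 2.5.4. If the sponsor prefers the single period, the SAP should give the reason and the protocol synopsis should carry the same exception clause as protocol 11.4.3.

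The cost is one SAP sentence and a second run of existing table programs. No new data are needed, and no clinical rule, test or sample size changes. Core-period counts for cardiovascular, renal and malignancy events will be small and should be read accordingly.
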